CSR	Clinical study report
CT	Computed tomography
CTCAE	Common Terminology Criteria for Adverse Event
CTLA-4	Cytotoxic T-lymphocyte-associated antigen 4
CV	Coefficient of variation
DCR	Disease control rate
DCO	Data cut off
DLT	Dose-limiting toxicity
DoR	Duration of response

Abbreviation or special term	Explanation
DRC	Data Review Committee
ECG	Electrocardiogram
eCRF	electronic case report form
FAS	Full analysis set
GeoSD	Geometric standard deviation
Gmean	Geometric mean
HCV	Hepatitis C virus
HIV	Human immunodeficiency virus
HLT	Higher-level terms
ICs	Immune cells
IHC	Immunohistochemistry
imAE	Immune-mediated adverse event
INRC	International Neuroblastoma Response Criteria
irAE	Immune-related adverse event
irRECIST	Immune-related Response Evaluation Criteria in Solid Tumors
KM	Kaplan-Meier
LD	Longest diameter
LLOQ	Lower limit of quantitation
MedDRA	Medical Dictionary for Regulatory Activities
MR	Minor response
MRI	Magnetic resonance imaging
MTD	Maximum tolerated dose
NA	Not applicable
NB	Neuroblastoma
NC	Not calculable
NCI	National Cancer Institute
NE	Not evaluable
NED	No evidence of disease
NK	Natural killer
NQ	Non-quantifiable
NTL	Non-target lesion
ORR	Objective response rate

Abbreviation or special term	Explanation
OS	Overall survival
OS12/24	Proportion of patients alive at 12 / 24 months from first dose of study treatment
PCR	Polymerase chain reaction
PD	Progression of disease
PD-L1	Programmed cell death ligand 1
PD-L2	Programmed cell death ligand 2
PFS	Progression-free survival
PK	Pharmacokinetics
PR	Partial response
PT	Preferred term
q4w	Every 4 weeks
RDI	Relative dose intensity
RECIST	Response Evaluation Criteria in Solid Tumors
RNA	Ribonucleic acid
RP2D	Recommended Phase II dose
SAE	Serious adverse event
SAP	Statistical Analysis Plan
SARC-1	Osteosarcoma and Ewing sarcoma
SARC-2	Rhabdomyosarcoma, non-rhabdomyosarcoma, and other sarcomas
SARCOMA	Osteosarcoma and Ewing sarcoma; soft-tissue sarcomas: Rhabdomyosarcoma, non-rhabdomyosarcoma, and other sarcomas
SAS	Safety analysis set
SD	Stable disease
SoA	Schedule of activities
SOC	System organ class
STD	Standard deviation
STO	Other solid tumors
TL	Target lesion
TSH	Thyroid stimulating hormone
ULN	Upper limit of normal

AMENDMENT HISTORY

Date	Brief description of change
08JUN2021	
There have been 3 protocol versions since the original SAP was created, updates as follows:
 
Section 1, updated to align objectives with protocol version 5. Study design and patient numbers updated to reflect cohorts removed and revised patient numbers in protocol version 5.
 
Section 3.1 updated to reflect new tumour assessment schedule and to remove references to cohorts removed in protocol version 5.
 
Section 3.3 removed references to ECG interval data as this is not being collected.
 
Section 3.5.1 and 3.5.2, references to the HL cohort were removed.
 
Section 4.2 layout of outputs for dose-finding part amended to include separate summaries by weight group.
 
Section 4.2.3.2 clarified that dose modification in AE outputs means interruption or discontinuation, as increases and decreases are not permitted.
 
Section 4.2.2, removed references to cohorts removed in protocol version 5. Clarified efficacy outputs are for dose-expansion only and accordingly removed references to INRC which is for the NB cohort enrolled in dose-finding only.
 
Section 4.2.5, COVID-19 pandemic related outputs have been added.
 
Section 4.2.3.5 removed reference to listing of physical examination data, as any physical examination findings are reported as adverse events.
 
Section 4.2.3.6 borderline ECG results added to reporting as a separate category.
 
CCI [REDACTED]
 
Section 5, patient numbers for the DRC updated in line with protocol version 5.

24JUN2021	
Section 2.1, amended the Evaluable for response analysis set and added the sensitivity analysis for unconfirmed ORR.
 
Section 3, removed INRC references throughout.
 
Section 3.2.2, amended the missed visits to account for the change to 16 weekly efficacy assessment being optional and clarified a RECIST visit response of NE does not count as a missed visit.
 
Section 3.3.4, changed BMI to BSA.
 
Section 4.2.2.1 and 4.2.2.6, clarified the mid-P approach is only required if the cohorts are expanded.
 
Section 4.2.3.4, removed the vital signs shift table.
 
Section 6, updated to include any relevant change detailed above.

Date	Brief description of change
17Nov2022	
Removed signature pages.
 
Section 2.1, more clarification provided for Evaluable for response analysis set, and only derive for Dose expansion phase.
 
Section 3.3.1 and 4.2.3.2, added AEPI.
 
Section 3.3.2 and 4.2.3.3, updated list of parameters with CTCAE grades and added detail for parameters with both low and high direction CTCAE grading.
 
Section 3.4.1 and 4.2.4.1. removed PK steady state.
 
Section 4.1.2, clarified derivation of baseline for questionnaires.
 
Section 4.2.7.2, removed efficacy repeat outputs CCI.
 
Section 4.2.4.3, clarified evaluable ADA samples for combination treatment for summaries.
 
Section 4.1.3 and 6, clarified upper limit of visit windowing for safety data.

19Apr2023	
Section 1.3, updated number of patients in STO cohort following CSP v6.
 
Section 2.2, removed the need for programmed important protocol deviations, these will come straight from the CTMS log.
 
Section 4.2.2.10 and 6, added analysis for dose-finding efficacy listing.
 
Section 4.2.3.2, removed imAE summary table of the Starting steroid dose and Time to first steroid dose, these are produced as listings
 
Section 4.2.3.4, removed VS change from baseline table to align with previous updates.
 
Section 4.2.4.1, reinstated text regarding PK figures.
 
Throughout, removed Non Hodgkin lymphoma (NHL) cohort from dose-expansion analysis following CSP v6.

1 STUDY DETAILS

This is the statistical analysis plan (SAP) for study D419EC00001. The SAP describes the statistical analyses specified in the clinical study protocol (CSP) version 6.0 in more detail; any changes with regards to what is already specified in the CSP will be described in Section **Error! Reference source not found.**

1.1 Study objectives

1.1.1 Primary objectives

Dose-finding phase

Primary Objective:	Outcome Measure:
To determine the adult equivalent exposure/ maximum tolerated dose (MTD) /recommended Phase II (pediatric) dose (RP2D) of durvalumab in combination with tremelimumab and durvalumab as monotherapy following combination therapy.	Pharmacokinetics (PK) parameters (including maximum serum concentration (C_{max}), minimum serum concentration (C_{min}), area under the curve (AUC), and others). Time of RP2D assessment will be at the end of the dose-finding phase, when sufficient numbers of evaluable samples have been accrued.
To determine the safety profile of durvalumab in combination with tremelimumab and durvalumab as monotherapy following combination therapy.	Adverse events (AEs), vital signs, physical examinations, electrocardiograms (ECGs), and laboratory evaluations.

Dose-expansion phase

Primary Objective:	Outcome Measure:
To determine the preliminary antitumor activity of durvalumab in combination with tremelimumab and durvalumab as monotherapy following combination therapy at the recommended dose, using cohort-specific response criteria (e.g. Response Evaluation Criteria in Solid Tumors (RECIST) 1.1).	Objective response rate (ORR) as determined by the Investigator assessed RECIST 1.1 or alternative pre-specified tumor-specific response rates for different scoring systems. Assessment of antitumor activity will be specific to tumor cohort. Additional efficacy endpoints that will be collected include DoR, BoR, DCR, PFS,

	APF12, and APF18 based on RECIST 1.1 assessed by the investigator, and OS, OS12, and OS24 as appropriate to each individual cohort.
--	---

1.1.2 Secondary objectives

Dose-finding and Dose-expansion Phase

Secondary Objective:	Outcome Measure:
To describe the PK of durvalumab and tremelimumab in combination and durvalumab as monotherapy following combination therapy in children and young adults with solid tumors.	Individual durvalumab and tremelimumab concentrations in serum, and PK parameters including C_{max} , C_{min} , AUC and other parameters where appropriate.
To determine the immunogenicity of durvalumab and tremelimumab in combination and durvalumab as monotherapy following combination therapy in children and young adults with solid tumors.	CCI
To measure effects on immune checkpoint inhibition in response to routine immunizations (dose-expansion phase only).	
To evaluate immune activation and counts of natural killer (NK)-, B- and T-cells	

1.1.3 Safety objectives

Safety Objective:	Outcome Measure:
To determine the safety profile and tolerability of patients from dose-expansion cohort(s) treated with durvalumab in combination with tremelimumab every 4 weeks (q4w).	AEs, vital signs, physical examinations, ECGs, and laboratory evaluations.

1.1.4 Exploratory objectives

Exploratory Objective:	Outcome Measure:
CCI	

1.2 Study design

This is an open-label, non-randomized, international, multicenter study investigating durvalumab in combination with tremelimumab (q4w for 4 cycles only) followed by durvalumab monotherapy (q4w) in pediatric patients from birth to <18 years of age with relapsed or refractory malignant solid tumors. Each treatment cycle is 28 days.

The study will be conducted in 2 sequential phases; a dose-finding phase (Phase I) followed by a disease specific dose-expansion phase (Phase II). The purpose of this study is to identify the recommended Phase II dose (RP2D) that will be taken forward to determine preliminary antitumor activity of durvalumab in combination with tremelimumab in solid malignant tumors, using disease specific response criteria.

Dose-finding phase

The dose-finding phase of the study will be conducted using a 3 + 3 design to determine whether durvalumab and tremelimumab can be administered safely in children and if adult exposures can be achieved. Pediatric patients with relapsed or refractory solid malignant tumors including osteosarcoma and Ewing sarcoma (SARC-1), rhabdomyosarcoma, non-rhabdomyosarcoma, and other sarcomas (SARC-2), neuroblastoma (NB), and other solid tumors (STO), will be enrolled in 2 arms based on patient weight:

[figure not shown]
- Arm A: patients weighing ≥ 35 kg
- Arm B: patients weighing < 35 kg

Three dose levels may be explored in each of the arms as outlined in [Figure 1](#). Dose level 1 will be 100% of the recommended adult dose of both durvalumab and tremelimumab administered as weight-adjusted doses. The doses and schedules are as follows:

- 1 Cycle 1 (durvalumab monotherapy): durvalumab 20 mg/kg
- 2 Cycles 2 to 5 (durvalumab in combination with tremelimumab): durvalumab 20 mg/kg and tremelimumab 1 mg/kg [4 cycles administered every 28 days]
- 3 From Cycle 6 onwards, treatment will continue until a discontinuation criterion is met, with durvalumab monotherapy administered at 20 mg/kg q4w.

At least one day between first patient and subsequent patients dosed at each dose-level is required.

Figure 1 Dose levels – Dose-finding phase

This figure shows the maximum doses for durvalumab at DLs 2 and 3 (40 mg/kg) and tremelimumab at DL 3 (2 mg/kg). Lower doses may be tested, depending on the obtained PK modeling data.

DL Dose level; NB Neuroblastoma; SARC-1 Osteosarcoma and Ewing sarcoma; SARC-2 Rhabdomyosarcoma, non-rhabdomyosarcoma, and other sarcomas; STO Solid tumor other.

A Data Review Committee (DRC) will be established prior to the initiation of the study to make decisions on dose escalations and determination of a recommended phase 2 dose (RP2D) to be further explored in the dose-expansion phase.

Dose escalation decisions will aim to identify the RP2D for durvalumab and tremelimumab in combination. Dose escalation decisions and determination of RP2D will mainly consider safety and PK information obtained from Cycle 1 (durvalumab monotherapy) and Cycle 2 (first administration of durvalumab and tremelimumab combined). This includes assessment of pre-defined dose-limiting toxicities (DLTs) in the first 2 cycles.

A de-escalation step may occur for durvalumab or/and tremelimumab, with reduced doses of 15 mg/kg and 0.75 mg/kg, respectively, if dose level 1 is considered not tolerated. Furthermore, if exposure of durvalumab or/and tremelimumab proves inadequate, intermediate dose levels may also be tested.

At least 1 patient representing each of the following pediatric age subsets will be enrolled: birth to 5 years, 6 to 11 years and 12 to <18 years. In addition, 3 patients older than 2 years of age must be treated with durvalumab in combination with tremelimumab and clear the DLT period and have been evaluated by the DRC before children less than 2 years old may be enrolled in the dose-finding phase.

[figure not shown]
The key considerations to be followed by the DRC during the dose-finding phase of the study are outlined in [Table 1](#):

Table 1 Key considerations for DRC

#DLTs	PK	Decision/Outcome
0 out of 3-5	Equivalent to adult exposure (5 out of 6 patients)	Declare tolerated and observed for 4 cycles, and if <2 patients with DLTs are observed during the first 4 cycles of study drug, enter dose-expansion stage
OR		
1 out of 6	<80% of adult exposure (≤2 patients)	Declare tolerated and move to next dose level.
1 out of 3		Increase number of patients to 6.
≥2		Declare not tolerated; if observed on dose level 1, move to dose level -1 (see Figure 2).

DLT dose limiting toxicity; DRC data review committee; PK pharmacokinetics.

Figure 2 Dose-finding: de-escalation schema

DL dose level.

A separate document (a DRC charter) will be created to detail all key tasks, working rules and timing of meetings of the DRC committee.

Dose-expansion phase

Once the RP2D has been established, recruitment into the dose-expansion study will be conducted using a Simon 2-stage optimal design with an additional provision to include 1 mixed disease cohort (other malignant solid tumors). Patients will be recruited into the cohorts outlined in [Table 2](#).

During dose-expansion, patients will be monitored for safety according to the same criteria employed during the dose-finding phase (although events will not be considered DLTs during dose-expansion). Additionally, 4 cycles of safety information are required prior to opening the initial dose-expansion cohorts. If during the treatment period, $\geq 33\%$ of patients experience safety events meeting the DLT criteria defined for the dose-finding phase (see CSP section 4.1.2), even if outside of the DLT evaluation period, enrollment may be paused, and study data will be reviewed to determine whether additional monitoring or alternative dose levels or schedules should be evaluated prior to further enrollment.

Table 2 Malignant solid tumor cohorts

Dose-finding phase	
Cohort	Type of cancer
SARC-1	Osteo sarcoma or Ewing sarcoma

SARC-2	Rhabdomyosarcoma, non-rhabdomyosarcoma soft-tissue sarcoma, other sarcomas
NB	Neuroblastoma
STO	Other solid tumors (not represented in the other solid tumor cohorts)

Dose-expansion phase

Cohort	Type of cancer
SARCOMA	bone sarcomas: osteosarcoma or Ewing Sarcoma; soft-tissue sarcomas [\geq 40% of enrollment]: Rhabdomyosarcoma, non-rhabdomyosarcoma and other sarcomas
STO	Other solid tumors (not represented in the other solid tumor cohorts)

STO Solid tumors other.

Disease specific cohorts will not be separated into weight-based arms, but patients within the expansion cohorts will be dosed according to the appropriate weight-based RP2D determined in the arms of dose-finding cohorts.

For the SARCOMA cohort, the initial stage will allow 11 evaluable patients, to be dosed in this disease-specific cohort. If 2 or more responses are observed, additional patients will be accrued, as part of the second stage, into the corresponding expansion cohort; 15 patients will be accrued into the SARCOMA expansion cohort for a total of 26 evaluable patients. If there has been ≤ 1 objective response in either cohort, at the time that evaluable patients (11 patients) dosed in the initial stage who have been followed for at least 3 cycles and have been assessed, the cohort will be discontinued for lack of benefit.

For the STO cohort, 10 evaluable patients will be enrolled into this mixed-disease cohort; Simon rules are not applicable for this cohort.

Duration of treatment and criteria for restarting treatment with durvalumab in combination with tremelimumab

All treatment will be administered beginning on Day 1 until clinical progression or confirmed radiological progression (refer to CSP Appendix E for solid tumors, CSP Appendix F for NB; other malignancies will be analyzed based on the best response assessed by the Investigator) unless there is unacceptable toxicity, withdrawal of consent, or another discontinuation criterion is met.

If during the durvalumab monotherapy component of the treatment (after the 4 cycles of durvalumab + tremelimumab, where applicable), a patient's disease progresses, re-administration of tremelimumab (in combination with durvalumab) for another 4 cycles may be considered, following the conditions below:

- Patients who complete the 4 dosing cycles of the combination of durvalumab and tremelimumab portion of the regimen (with clinical benefit as per Investigator judgement) but subsequently have evidence of defined PD, with or without confirmation, during the durvalumab monotherapy portion of the combination regimen may restart treatment with the combination once (4 cycles only). After this, durvalumab monotherapy will resume, if the Investigator judges there is clinical benefit to the patient.

1.3 Number of patients

Dose-finding phase

The final sample size in the dose-finding phase will depend on the number of DLTs and on the number of dose levels to be explored. In addition, any patients not evaluable (NE) will be replaced in order to have the required number of patients evaluable at each dose level. A minimum of 12 patients is anticipated to be dosed, to enable exploration of 1 dose level in both patients weighing 35 kg and greater, and patients weighing under 35 kg. If all 3 dose levels are used at both weight-based arms, then 36 evaluable patients would be necessary to complete the dose-finding phase. If approximately 20% of patients need to be replaced due to non-evaluability, then a maximum of 45 patients will be enrolled on the dose-finding cohorts.

Dose-expansion phase

For the dose-expansion phase, the SARCOMA cohort will follow a Simon 2-stage optimal design. An ORR $\leq 10\%$ will not be considered clinically meaningful.

In the SARCOMA cohort, the Simon 2-stage design will have a type I error rate set at 0.1 (1-sided) and power of at least 85%. Based on the assumption that the ORR for the null hypothesis is 10% and the true ORR for the SARCOMA cohort is 30%, then the SARCOMA cohort will require a total of 26 evaluable patients (with the requirement that $\geq 40\%$ of the patients enrolled must have soft-tissue sarcomas), with 11 evaluable patients required in the first stage. If fewer than 2 confirmed responses are observed in the first 11 evaluable patients, then the cohort will be closed for lack of benefit. If 2 or more responses are observed out of the first 11 evaluable patients, then an additional 15 evaluable patients will be enrolled, for a total of 26 evaluable patients.

For a cohort that enrolls the maximum evaluable patients for that particular cohort (26 in the SARCOMA cohort), if fewer than 5 responses are observed out of the maximum total of evaluable patients, then no further investigation of that cohort will be done; if 5 or more responses are observed out of the maximum total of evaluable patients, then the null hypothesis will be rejected for this cohort and further investigation will be warranted.

The STO cohort is planned to recruit 10 evaluable patients. This sample size is based on practical, rather than formal considerations, as no formal hypothesis testing is planned for this cohort.

With the above considerations, the sample size for evaluable patients in the dose-expansion phase is expected to range from 21 to 36. Assuming that about 20% of patients may not be evaluable for ORR, the total number of patients dosed in the dose-expansion phase may range from approximately 25 to 43.

2 ANALYSIS SETS

2.1 Definition of analysis sets

Details of the analysis sets are presented in [Table 3](#) and [Table 4](#).

Table 3 Analysis sets

Analysis Set	Definition	Phase derived for
Full analysis set (FAS)	The FAS will include all patients who were assigned to treatment and received at least 1 dose of study treatment. The FAS (or subset of the FAS specified below) will be used for all efficacy analyses.	Dose-finding and Dose-expansion
Evaluable for response analysis set	
The subset of patients in the FAS who had
 
 • measurable disease (per RECIST 1.1) at baseline 
 ○ and had at least one follow-up scan measuring all required target lesions ○ and have been followed for at least 3 cycles (to allow for a confirmatory scan at 4 weeks after the first assessment scan) 
OR
 
 • measurable disease (per RECIST 1.1) at baseline 
 ○ and progressed or died in the absence of a follow-up scan. 	Dose-expansion
Safety analysis set (SAS)	The SAS will consist of all patients who received any amount of study treatment. Safety data will be summarized using the SAS according to the treatment received.	Dose-finding and Dose-expansion

Table 3 Analysis sets

Analysis Set	Definition	Phase derived for
Dose-limiting toxicity (DLT) evaluable analysis set	The DLT evaluable analysis set is a subset of the SAS for the dose-finding phase of the study. It includes all patients enrolled in the dose-finding phase of the study who receive the protocol-assigned treatment with durvalumab + tremelimumab and complete the safety follow-up through the DLT evaluation period (Cycle 1 + Cycle 2) or experience a DLT during the DLT evaluation period.	Dose-finding
PK analysis set	All patients who receive at least 1 dose of study treatment per the CSP for whom any post dose data are available and who do not violate or deviate from the CSP in ways that would significantly affect the PK analyses will be included in the PK analysis set. The population will be defined by the Study Physician, Pharmacokineticist, and Statistician prior to any analyses being performed.	Dose-finding and Dose-expansion
ADA analysis set	All patients who receive at least 1 dose of study treatment per the CSP for whom baseline, and any post dose data are available will be included in the ADA analysis set.	Dose-finding and Dose-expansion

Table 4 Summary outcome variables and analysis sets

Outcome variable	Analysis set
Efficacy Data	
ORR (primary for dose-expansion phase [confirmed responses])	Evaluable for response analysis set (Sensitivity analysis on FAS)
ORR (unconfirmed responses)	(Sensitivity analysis on Evaluable for response analysis set)
PFS, OS, BoR (confirmed responses), APF12, APF18, OS12, OS24	FAS
DoR	Evaluable for response analysis set (restricted to confirmed responders only)
DCR	Evaluable for response analysis set (Sensitivity analysis on FAS)

Table 4 Summary outcome variables and analysis sets

Outcome variable	Analysis set
Demography	FAS
PK data	PK analysis set
ADA data	ADA analysis set
Safety Data	
Exposure	SAS
AEs	SAS
Laboratory measurements	SAS
Vital Signs	SAS
DLTs (primary for dose-finding phase)	DLT evaluable analysis set

AE Adverse event; APF12 / APF18 Proportion of patients alive and progression-free at 12 / 18 months from first dose of study treatment; BoR Best objective response; DCR Disease control rate; DLT Dose-limiting toxicity; DoR Duration of response; FAS Full analysis set; OS Overall survival; ORR Objective response rate; OS12 / OS24 Proportion of patients alive at 12 / 24 months from first dose of study treatment; PFS Progression-free survival; PK Pharmacokinetics; SAS Safety analysis set.

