9.3.2 Evaluable for response analysis set

The subset of patients in the FAS who had measurable disease at baseline.

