4 ANALYSIS METHODS

4.1 General principles

The primary analysis cut off will be defined at approximately 6 months after enrollment of the last patient. At this point, data analysis will be performed, and the CSR will be written. After this, patients still in the study will continue to be followed and a CSR addendum will be issued for OS and safety data collection.

For PK and other biomarkers, the sample bioanalysis will be performed by AstraZeneca or a contracted laboratory. PK parameters will be derived by Labcorp. The merging of PK concentration data with actual elapsed time from dose for PK sampling times will be performed by IQVIA Programming. The PK summaries and data listings will be the responsibility of IQVIA Biostatistics.

Statistical summaries and analyses of non-PK data will be performed by IQVIA under the direction of the Biostatistics Group, AstraZeneca using SAS® version 9.4 or higher and, where appropriate, additional validated software.

There is no formal statistical testing for the dose-finding phase of the study.

The dose-expansion phase of the study will formally test the following hypothesis:

- H_0 : ORR \leq 10%
- H_1 : ORR $>$ 10%.

The test will be done at the 1-sided 5% level and it will be performed for the SARCOMA cohort.

No formal statistical testing will be performed for the STO cohort.

For the dose-finding phase, and dose-expansion phase where relevant, dose levels will be labelled in summary tables as:

- durvalumab xx mg/kg + tremelimumab xx mg/kg

with xx depending on the dose levels used.

For the dose-expansion phase, cohorts will be labelled in summary tables as:

- SARCOMA
- STO

Total columns will be included for the dose-finding and dose-expansion phases separately for outputs where a total column is required.

Visits will be present as cycle and day (e.g. Cycle 1 Day 1). Study day will be calculated as follows:

Days prior to first dose: Study day = date – first dose date

Days on or after first dose: Study day = date – first dose date + 1

First dose refers to either durvalumab or tremelimumab, whichever was administered first. Dates of progression will not be imputed.

The end of study is defined as the last expected visit/contact of the last patient undergoing the study. A patient is considered to have completed the study when he/she has completed his/her last scheduled visit shown in the schedule of activities (CSP section 1.1).

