5 INTERIM ANALYSES

No formal interim analysis for efficacy is planned for this study. However, in dose-expansion phase, ORR will be evaluated on an ongoing basis for the first 11 evaluable patients (SARCOMA cohort) to complete Stage 1 of the Simon 2-Stage optimal design (see Section 4.1.4 of the CSP). The methodology described in this SAP for the derivation of visit responses and efficacy variables will also be used for the DRC analyses. Further information around the analysis and outputs required to facilitate this will be described in the DRC charter.

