6 CHANGES OF ANALYSIS FROM PROTOCOL

As there is no current plan to incorporate irRECIST, this has not been referenced in the SAP.

The definition of the evaluable for response analysis set has been updated to align with the definition in the DRC charter.

An additional sensitivity analysis of ORR using unconfirmed responses has been added.

Clarification has been added that the mid-P methodology is applicable only if the cohorts are expanded.

Visit windowing of safety domains will be considered up to end of treatment, rather than up to progression as mentioned in the protocol.

An additional efficacy listing detailing dose-finding cohort overall RECIST response per investigator assessment has been added.

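### Read literally, the SAP's evaluable-for-response set leaves out a patient who has a complete first scan and then dies before 3 cycles but keeps one who dies unscanned, which tilts primary ORR and the Simon count slightly upward

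*SAP*

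**What the plan says.** Protocol 9.3.2 defines the set simply: "The subset of patients in the FAS who had measurable disease at baseline". SAP 2.1, Table 3 narrows it for dose-expansion. Both routes need measurable disease at baseline.

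- Route 1 adds a complete follow-up scan, with every target lesion measured, and a follow-up condition: "and have been followed for at least 3 cycles (to allow for a confirmatory scan at 4 weeks after the first assessment scan").
- Route 2 adds "and progressed or died in the absence of a follow-up scan".

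SAP 6 declares the change: "The definition of the evaluable for response analysis set has been updated to align with the definition in the DRC charter". The charter is not among the documents reviewed.

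SAP Table 4 makes this set the denominator of the primary ORR. SAP 1.3 counts evaluable patients in the SARCOMA cohort: continue with 2 or more responses in 11, reject the null with 5 or more in 26. There, "the Simon 2-stage design will have a type I error rate set at 0.1 (1-sided) and power of at least 85" percent. SAP 5 carries the derivations into the Stage 1 look: "The methodology described in this SAP for the derivation of visit responses and efficacy variables will also be used for the DRC analyses".

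**The concern.** Take two patients with measurable disease, neither of whom responds. One dies on day 40 without a scan and enters by route 2 as a non-responder. The other has a complete scan on day 56 and dies on day 70. Follow-up fell short of 3 cycles, so route 1 fails; a scan exists, so route 2 fails. The SAP gives no reason for treating them differently, and the protocol definition keeps both. The same gap takes in a patient whose scan shows progression and who is then lost to follow-up because of the disease before 3 cycles.

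Inclusion then depends partly on outcome. Because the rule counts 11 and 26 evaluable patients, each patient left out is replaced. At stake are the primary ORR and the error rate of the go/no-go rule, in a cohort so small that one patient's status can change the result.

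**Working it through.** **1. Who falls in the gap.** A cycle is 28 days, so 3 cycles are 84 days. The first scan is due at week 8 ± 1 week, day 49 to 63 (Protocol Table 2). A response must be confirmed at least 4 weeks later (SAP 3.2.1), so the earliest on-schedule confirmation is day 49 + 28 = 77. A patient who dies before day 84 is therefore almost never a confirmed responder; the exceptions need a confirming scan on days 77 to 83 or early unscheduled scans. Stopping treatment alone does not put a patient in the gap, because Protocol 7.1.1 keeps such patients in follow-up.

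**2. The plan's own design.** P(reject | p) = Σ over x = 2 to 11 of P(Bin(11, p) = x) × P(Bin(15, p) ≥ max(0, 5 − x)). At p = 0.10 this gives 0.0865; at p = 0.30 it gives 0.8516. Both meet SAP 1.3.

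**3. Share dropped, literal reading.** The documents give no early death rate for this population. As an assumption, use the 9.2-month median OS that Protocol 2.2.1 quotes for another checkpoint inhibitor in a different pediatric population, exponential survival, every death in the window preceded by a complete scan, and withdrawals not counted. Then λ = ln 2 / (9.2 × 30.4375) = 0.002475 per day, and for a first scan on day s the share is d = exp(−λs) − exp(−84λ). For s = 56: 0.8706 − 0.8123 = 0.0583.

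**4. Effect on the rule.** If those dropped are non-responders and are replaced, ORR among those kept is p/(1 − d). For p = 0.10 and s = 56: 0.10/0.9417 = 0.1062. This goes into the formula in step 2.

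| Hazard | First scan | Dropped | Per 26 dosed | ORR read when true ORR is 10% | Type I error |
|---|---|---|---|---|---|
| Full | week 9 | 4.3% | 1.1 | 10.5% | 0.100 |
| Full | week 8 | 5.8% | 1.5 | 10.6% | 0.105 |
| Full | week 7 | 7.4% | 1.9 | 10.8% | 0.111 |
| Half | week 9 | 2.4% | 0.6 | 10.2% | 0.094 |
| Half | week 8 | 3.2% | 0.8 | 10.3% | 0.096 |
| Half | week 7 | 4.0% | 1.0 | 10.4% | 0.099 |

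Type I error reaches 0.10 when 4.35% are dropped (the first row is 0.09996 before rounding). At a true ORR of 30% and d = 5.8%, the set would read 0.30/0.9417 = 31.9%.

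**5. Two other readings.** Route 2 can be parsed as progressed, or died without a scan. Every progressor is then kept. If half of the deaths in the window had progression on the scan (an assumption), d halves: 2.2%, 2.9% and 3.7% at the full hazard, with type I error 0.093, 0.095 and 0.098; and 1.2%, 1.6% and 2.0% at half hazard, with 0.090, 0.091 and 0.092. Alternatively, the 3-cycle condition may mean potential follow-up. SAP 4.1 says "The primary analysis cut off will be defined at approximately 6 months after enrollment of the last patient". Six months is about 183 days, well beyond 84, so at that cutoff the condition excludes nobody.

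**The case against.** The best defence is that the 3 cycles are a timing condition. The Protocol synopsis, Protocol 4.1.4 and SAP 1.2 all use similar wording to say when the Stage 1 look may happen. SAP 1.2 speaks of patients "dosed in the initial stage who have been followed for at least 3 cycles and have been assessed", already calling them evaluable. The parenthesis in Table 3 gives a timing purpose, and the charter may define the term. This stands as a plausible reading, under which the condition has no effect at the primary cutoff. But the SAP does not define it, and Table 3 as worded does not say potential. Even on this reading, a patient whose only scan missed a target lesion and who then died fails both routes.

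The hazard is borrowed, and inclusion criterion 9 in Protocol 5.1.1 requires a life expectancy of at least 3 months. That favors the lower rows of the table. It also stands.

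The reporting risk is partly covered. The change is declared, ORR is repeated on the FAS (SAP Table 4 and 4.2.2.1), and confirmed BoR is tabulated on the FAS (SAP 4.2.2.5). These show the effect on the estimate but do not correct the 11/26 count. That count is not the only input to expansion: under Protocol 9.6.1 the DRC also weighs safety and PK.

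A reader might infer that every withdrawal or loss inflates ORR. It does not: leaving out patients lost for reasons unrelated to disease carries no upward bias in itself. A reader might also take the condition to mean 3 cycles on treatment, which would make the gap far larger; Protocol 7.1.1 speaks against that.

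**Conclusion.** The gap is real on the literal wording, and its direction is upward for deaths and disease-driven losses. The size is small: under the step 3 assumptions, about 2% to 7% dropped, an ORR of 10% read as 10.2% to 10.8%, and type I error of 0.094 to 0.111 against 0.087 as designed. The alternative parse of route 2 gives less, and the potential-follow-up reading gives none from this condition at the primary cutoff.

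A reader might conclude that the 0.10 error rate is breached. The documents do not support that. It is passed only when more than 4.35% are dropped, which needs the literal reading together with a borrowed hazard at its full value. The one-sided 5% level in SAP 4.1 is a separate conflict, since the unmodified rule at 0.0865 already exceeds it.

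**What to change.** - Reword route 2 so that it admits any patient with measurable disease at baseline who progressed or died before completing 3 cycles, whether or not a follow-up scan exists, and counts that patient as a non-responder unless a response was already confirmed.
- State that the 3-cycle condition in route 1 means potential follow-up and serves to time the Stage 1 look.
- Bring the DRC charter into line.

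This is wording only and needs no new data. ORR may read slightly lower. Potential follow-up also brings in by route 1 the few patients with a complete scan who leave for unrelated reasons, so the SAP should say how they are counted.

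Restoring the full Protocol 9.3.2 set, or counting all unrelated losses as non-responders, is optional because it costs power. With a share x of would-be responders lost, power is the step 2 formula at 0.30 × (1 − x): 0.845 at 1%, 0.819 at 5% and 0.780 at 10%. It falls below 85% once x exceeds 0.26%. That route would also mean re-basing the 20% non-evaluable allowance in SAP 1.3.
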